##### **Measurability of Tumor at Baseline Definitions**

At baseline, tumor lesions/lymph nodes will be categorized as measurable or non-measurable as follows:

##### **Measurable**

Tumor lesions: Must be accurately measured in at least one dimension (longest diameter in the plane of measurement is to be recorded) with a minimum size of:

- 10 mm by CT scan (CT scan slice thickness no greater than 5 mm)
- 10 mm caliper measurement by clinical examination (lesions which cannot be accurately measured with calipers should be recorded as non-measurable)
- 20 mm by chest X-ray

Measurable malignant lymph nodes: To be considered pathologically enlarged and measurable, a lymph node must be  $\geq 15$  mm in the short axis when assessed by CT scan (CT scan slice thickness is recommended to be no greater than 5 mm). At baseline and in follow-up, only the short axis will be measured and followed. See also notes below on “Baseline documentation of target and non-target lesions” for information on lymph node measurement.

### **Non-measurable**

All other lesions, including small lesions (longest diameter <10 mm or pathological lymph nodes with  $\geq 10$  to <15 mm short axis) as well as truly non-measurable lesions. Lesions considered truly non-measurable include: leptomeningeal disease, ascites, pleural or pericardial effusion, inflammatory breast disease, lymphangitic involvement of skin or lung, abdominal masses/abdominal organomegaly identified by physical examination that is not measurable by reproducible imaging techniques.

### **Special Considerations Regarding Lesion Measurability**

Bone lesions, cystic lesions, and lesions previously treated with local therapy require particular comment:

#### **Bone lesions:**

- Bone scan, PET scan or plain films are not considered adequate imaging techniques to measure bone lesions. However, these techniques can be used to confirm the presence or disappearance of bone lesions.
- Lytic bone lesions or mixed lytic-blastic lesions, with identifiable soft tissue components, that can be evaluated by cross sectional imaging techniques such as CT or MRI can be considered as measurable lesions if the soft tissue component meets the definition of measurability described above.
- Blastic bone lesions are non-measurable.

#### **Cystic lesions:**

- Lesions that meet the criteria for radiographically defined simple cysts should not be considered as malignant lesions (neither measurable nor non-measurable) since they are, by definition, simple cysts.
- ‘Cystic lesions’ thought to represent cystic metastases can be considered as measurable lesions, if they meet the definition of measurability described above. However, if noncystic lesions are present in the same subject, these are preferred for selection as target lesions.

#### **Lesions with prior local treatment:**

- Tumor lesions situated in a previously irradiated area, or in an area subjected to other loco-regional therapy, are not considered measurable unless there has been demonstrated progression in the lesion since the therapy.

### **Specifications by Methods of Measurements**

#### **Measurement of Lesions**

All measurements should be recorded in metric notation, using calipers if clinically assessed. All baseline evaluations should be performed as close as possible to the treatment start and NEVER more than 4 weeks before the beginning of the treatment.

## **Method of Assessment**

The same method of assessment and the same technique should be used to characterize each identified and reported lesion at baseline and during follow-up. Imaging-based evaluation should always be done rather than clinical examination unless the lesion(s) being followed cannot be imaged but are assessable by clinical examination.

CT, MRI: CT is the best currently available and reproducible method to measure lesions selected for response assessment. This guideline has defined measurability of lesions on CT scan based on the assumption that CT slice thickness is 5 mm or less. When CT scans have slice thickness greater than 5 mm, the minimum size for a measurable lesion should be twice the slice thickness. MRI is also acceptable in certain situations (eg, for body scans).

## **Tumor Response Evaluation**

### **Assessment of Overall Tumor Burden and Measurable Disease**

To assess objective response or future progression, it is necessary to estimate the overall tumor burden at baseline and use this as a comparator for subsequent measurements.

In this study, only subjects with measurable disease at baseline should be included in the study.

### **Baseline Documentation of ‘Target’ and ‘Non-Target’ Lesions**

When more than one measurable lesion is present at baseline all lesions up to a total of two lesions per organ and a maximum of five lesions total representative of all involved organs should be identified as target lesions and will be recorded and measured at baseline (this means in instances where subjects have only one or two organ sites involved a maximum of two and four lesions, respectively, will be recorded).

Target lesions should be selected on the basis of their size (lesions with the longest diameter), be representative of all involved organs, but in addition should be those that lend themselves to reproducible repeated measurements. It may be the case that, on occasion, the largest lesion does not lend itself to reproducible measurement in which circumstance the next largest lesion which can be measured reproducibly should be selected.

Lymph nodes merit special mention since they are normal anatomical structures which may be visible by imaging even if not involved by tumor. As noted above, pathological nodes which are defined as measurable and may be identified as target lesions must meet the criterion of a short axis of  $\geq 15$  mm by CT scan. Only the short axis of these nodes will contribute to the baseline sum. The short axis of the node is the diameter normally used by radiologists to judge if a node is involved by solid tumor. Nodal size is normally reported as two dimensions in the plane in which the image is obtained (for CT scan this is almost always the axial plane; for MRI the plane of acquisition may be axial, sagittal, or coronal). The smaller of these measures is the short axis. For example, an abdominal node which is reported as being 20 mm  $\times$  30 mm has a short axis of 20 mm and qualifies as a malignant, measurable node. In this example, 20 mm should be recorded as the node measurement. All other pathological nodes (those with short axis  $\geq 10$  mm but  $< 15$  mm) should be considered non-target lesions. Nodes that have a short axis  $< 10$  mm are considered non-pathological and should not be recorded or followed.

A sum of the diameters (longest for non-nodal lesions, short axis for nodal lesions) for all target lesions will be calculated and reported as the baseline sum of diameters. If lymph nodes are to be included in the sum, then as noted above, only the short axis is added into the sum. The baseline sum of diameters will be used as reference to further characterize any objective tumor regression in the measurable dimension of the disease.

All other lesions (or sites of disease) including pathological lymph nodes should be identified as non-target lesions and should also be recorded at baseline. Measurements are not required and these lesions should be followed as ‘present’, ‘absent’, or in rare cases ‘unequivocal progression’. In addition, it is possible to record multiple non-target lesions involving the same organ as a single item on the case record form (eg, ‘multiple enlarged pelvic lymph nodes’ or ‘multiple liver metastases’).

### **Evaluation of Target Lesions**

**Complete Response (CR):** Disappearance of all target lesions. Any pathological lymph nodes (whether target or non-target) must have reduction in short axis to <10 mm.

**Partial Response (PR):** At least a 30% decrease in the sum of diameters of target lesions, taking as reference the baseline sum of diameters.

**Progressive Disease (PD):** At least a 20% increase in the sum of diameters of target lesions, taking as reference the smallest sum on study (this includes the baseline sum if that is the smallest on study). In addition to the relative increase of 20%, the sum must also demonstrate an absolute increase of at least 5 mm. (Note: the appearance of one or more new lesions is also considered progression.)

**Stable Disease:** Neither sufficient shrinkage to qualify for PR nor sufficient increase to qualify for PD, taking as reference the smallest sum of diameters while on study.

### **Special Notes on the Assessment of Target Lesions**

**Lymph nodes:** Lymph nodes identified as target lesions should always have the actual short axis measurement recorded (measured in the same anatomical plane as the baseline examination), even if the nodes regress to below 10 mm on study. This means that when lymph nodes are included as target lesions, the ‘sum’ of lesions may not be zero even if CR criteria are met, since a normal lymph node is defined as having a short axis of <10 mm. For PR, SD, and PD, the actual short axis measurement of the nodes is to be included in the sum of target lesions.

**Target lesions that become ‘too small to measure’:** While on study, all lesions (nodal and non-nodal) recorded at baseline should have their actual measurements recorded at each subsequent evaluation, even when very small (eg, 2 mm). However, sometimes lesions or lymph nodes which are recorded as target lesions at baseline become so faint on CT scan that the radiologist may not feel comfortable assigning an exact measure and may report them as being ‘too small to measure’. When this occurs, it is important that a value be recorded on the eCRF. If it is the opinion of the radiologist that the lesion has likely disappeared, the measurement should be recorded as 0 mm. If the lesion is believed to be present and is faintly seen but too small to measure, a default value of 5 mm should be assigned. (Note: It is unlikely that this rule will be used for lymph nodes since they usually have a definable size when normal and are frequently surrounded by fat such as in the retro-peritoneum.) This default value is derived from

the 5 mm CT slice thickness (but should not be changed with varying CT slice thickness.) The measurement of these lesions is potentially non-reproducible; therefore providing this default value will prevent false responses or progressions based upon measurement error.

If the radiologist is able to provide an actual measurement, that should be recorded, even if it is below 5 mm.

**Lesions that split or coalesce on treatment:** When non-nodal lesions ‘fragment’, the longest diameters of the fragmented portions should be added together to calculate the target lesion sum. Similarly, as lesions coalesce, a plane between them may be maintained that would aid in obtaining maximal diameter measurements of each individual lesion. If the lesions have truly coalesced such that they are no longer separable, the vector of the longest diameter in this instance should be the maximal longest diameter for the ‘coalesced lesion’.

### **Evaluation of Non-Target Lesions**

**Complete Response (CR):** Disappearance of all non-target lesions and normalization of tumor marker level. All lymph nodes must be non-pathological in size (<10 mm short axis).

**Non-CR/Non-PD:** Persistence of one or more non-target lesion(s) and/or maintenance of tumor marker level above the normal limits.

**Progressive Disease (PD):** Unequivocal progression (see comments below) of existing non-target lesions. (Note: the appearance of one or more new lesions is also considered progression.)

### **Special Notes on Assessment of Progression of Non-target Disease**

The concept of progression of non-target disease requires additional explanation as follows, when the subject also has measurable disease. In this setting, to achieve ‘unequivocal progression’ on the basis of the non-target disease, there must be an overall level of substantial worsening in non-target disease such that, even in presence of SD or PR in target disease, the overall tumor burden has increased sufficiently to merit discontinuation of therapy. A modest ‘increase’ in the size of one or more non-target lesions is usually not sufficient to qualify for unequivocal progression status. The designation of overall progression solely on the basis of change in non-target disease in the face of SD or PR of target disease will therefore be extremely rare.

### **New Lesions**

The appearance of new malignant lesions denotes disease progression; therefore, some comments on detection of new lesions are important. There are no specific criteria for the identification of new radiographic lesions; however, the finding of a new lesion should be unequivocal: ie, not attributable to differences in scanning technique, change in imaging modality, or findings thought to represent something other than tumor (for example, some ‘new’ bone lesions may be simply healing or flare of pre-existing lesions). This is particularly important when the subject’s baseline lesions show partial or complete response. For example, necrosis of a liver lesion may be reported on a CT scan report as a ‘new’ cystic lesion, which it is not.

A lesion identified on a follow-up study in an anatomical location that was not scanned at baseline is considered a new lesion and will indicate disease progression. An example of this is the subject who has visceral disease at baseline and while on study has a CT or MRI of the brain which reveals metastases. The subject’s brain metastases are considered to be evidence of PD even if he/she did not have brain imaging at baseline.

If a new lesion is equivocal, for example because of its small size, continued therapy and follow-up evaluation will clarify if it represents truly new disease. If repeat scans confirm there is definitely a new lesion, then progression should be declared using the date of the initial scan that indicated its presence.

### Evaluation of Best Overall Response

The best overall response is the best response recorded from the start of the study treatment until the EOT. Confirmatory measurement for CR or PR is required in this study. The subject’s best overall response assignment will depend on the findings of both target and non-target disease and will also take into consideration the appearance of new lesions.

### Time Point Response

It is assumed that at each protocol-specified time point, a response assessment occurs. [Table 10.4](#) provides a summary of the overall response status calculation at each time point for subjects who have measurable disease at baseline.

All post-baseline scans must be anchored against the baseline (Cycle 1 Day 1) scan.

**Table 10.4: Time Point Response: Subjects With Target (±Non-Target) Disease**

Target lesions	Non-target lesions	New lesions	Overall response
CR	CR	No	CR
CR	Non-CR/non-PD	No	PR
CR	Not evaluated	No	PR
PR	Non-PD or not all evaluated	No	PR
Stable disease	Non-PD or not all evaluated	No	Stable disease
Not all evaluated	Non-PD	No	NE
PD	Any	Yes or No	PD
Any	PD	Yes or No	PD
Any	Any	Yes	PD

CR = complete response; PR = partial response; PD = progressive disease; and NE = not evaluable

### Missing Assessments and In-evaluable Designation

When no imaging/measurement is done at all at a particular time point, the subject is NE at that time point. If only a subset of lesion measurements is made at an assessment, usually the case is also considered NE at that time point, unless a convincing argument can be made that the contribution of the individual missing lesion(s) would not change the assigned time point response. This would be most likely to happen in the case of PD. For example, if a subject had a

baseline sum of 50 mm with three measured lesions and at follow-up only two lesions were assessed, but those gave a sum of 80 mm, the subject will have achieved PD status, regardless of the contribution of the missing lesion.

### Best Overall Response: All Time Points

The best overall response is determined once all the data for the subject are known. The BOR when confirmation of CR or PR is required is displayed in [Table 10.5](#).

**Table 10.5: Best Overall Response When Confirmation of CR and PR Required**

Overall response		Overall response
First time point	Subsequent time point	Best
CR	CR	CR
CR	PR	SD, PD or PR a
CR	SD	SD, provided minimum criteria for SD duration met, otherwise, PD
CR	PD	SD, provided minimum criteria for SD duration met, otherwise, PD
CR	NE	SD, provided minimum criteria for SD duration met, otherwise, PD
PR	CR	PR
PR	PR	PR
PR	SD	SD
PR	PD	SD, provided minimum criteria for SD duration met, otherwise, PD
PR	NE	SD, provided minimum criteria for SD duration met, otherwise, PD
NE	NE	NE

CR = complete response; NE = not evaluable; PD = progressive disease; PR = partial response; SD = stable disease

a If a CR is truly met at first time point, then any disease seen at a subsequent time point, even disease meeting PR criteria relative to baseline, makes the disease PD at that point (since disease must have reappeared after CR).

Best response would depend on whether minimum duration for SD was met. However, sometimes ‘CR’ may be claimed when subsequent scans suggest small lesions were likely still present and in fact the subject had PR, not CR at the first time point. Under these circumstances, the original CR should be changed to PR and the best response is PR.

Source: Eisenhauer EA, Therasse P, Bogaerts J, et al. New response evaluation criteria in solid tumours: Revised RECIST guideline (v1.1). Table 3. Euro J Can. 2009;45:228-47.

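### In Table 10.5, a CR or PR followed only by a not-evaluable scan becomes a best response of PD when the SD minimum is not met, although no progression was observed

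*Combined protocol and SAP*

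**What the plan says.** Protocol Section 10.4 (Best Overall Response: All Time Points) makes Table 10.5 the rule for BOR when CR and PR must be confirmed. In the rows CR then NE and PR then NE the assigned BOR is "SD, provided minimum criteria for SD duration met, otherwise, PD". The same wording stands in the rows CR then SD, CR then PD and PR then PD.

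Other parts of the appendix bear on the two NE rows:

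- **Missing scan:** "When no imaging/measurement is done at all at a particular time point, the subject is NE at that time point".
- **Incomplete scan:** "If only a subset of lesion measurements is made at an assessment, usually the case is also considered NE at that time point". The exception is a case where the missing lesions could not change the result, for example when the lesions that were measured already establish PD. Table 10.4 agrees: target lesions not all evaluated, no non-target progression and no new lesion give NE.
- **PD, target lesions:** "At least a 20% increase in the sum of diameters of target lesions, taking as reference the smallest sum on study", with an absolute increase of at least 5 mm.
- **PD, non-target lesions:** "Unequivocal progression (see comments below) of existing non-target lesions".
- **PD, new lesions:** "The appearance of new malignant lesions denotes disease progression".
- **BOR:** "The best overall response is the best response recorded from the start of the study treatment until the EOT".
- **Footnote a of Table 10.5**, on PD after a CR: "any disease seen at a subsequent time point, even disease meeting PR criteria relative to baseline, makes the disease PD at that point".

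The minimum SD duration is invoked in the table and its footnote, but no number of weeks appears anywhere in the document.

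**The concern.** In a CR-then-NE or PR-then-NE sequence the only readable post-baseline result is a response, and the next scan is missing or unreadable. Neither time point records progression. If the response came before the SD minimum, the table nevertheless returns PD.

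Two things are at stake. The BOR distribution would show too much primary progression and too few not-evaluable subjects. A subject could also carry a BOR of PD while the PFS record holds no progression date, which is an inconsistency that a reader of the study report would have to query.

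**Working it through.** The plan gives no figure for this point, so the check is mainly a comparison of texts, followed by a check on what changes and how far the branch reaches.

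**1. Does any definition produce PD in these two rows?**

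- The second time point is NE by assumption. If the measured lesions had established progression, the time point would be PD and the row would be PR then PD or CR then PD.
- The first time point is CR or PR.
- None of the three routes to PD (target growth, non-target progression, new lesion) has been observed, so PD cannot be the best response recorded. Section 9.5.1.1 ends the BOR window differently, at documented progression or new anticancer treatment, but no PD is recorded in that window either.
- Footnote a justifies PD after CR because disease was seen again. A not-evaluable scan shows no such thing, and the footnote is attached to the CR-then-PR row.
- The rows CR then SD, CR then PD and PR then PD rest on disease or progression that was seen. They are not in question.

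**2. Is the table consistent with itself?**

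- NE then NE gives NE, so NE is an available BOR category.
- PR then SD gives SD with no proviso. A subject seen to lose PR status is always SD, while a subject with the same PR and an unreadable second scan can become PD.

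**3. Which analyses change if the fallback is NE?**

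- ORR: Section 9.5.1.1 counts a BOR of NE as non-response, and PD is also non-response. The numerator and denominator are unchanged.
- The primary test is therefore unchanged. For context, with n = 210 and a null ORR of 26.4%, the exact rule rejects at 69 responders (32.9%), with upper-tail probability 0.0222 and power 0.907 at 37%. This agrees with the approximately 91% in Section 9.3.
- DCR: only confirmed CR, confirmed PR and SD count (Section 9.5.1.2). PD and NE are both outside.
- PFS and DoR: events are documented progression or death (Section 9.5.1.2). A BOR of PD with no progression date should create no event.
- BOR distribution: each affected subject moves 1/210 = 0.48 points.

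An illustration with assumed counts, not a forecast: 210 subjects, 77 responders, 70 SD, 50 PD and 13 NE, with 10 subjects moved from PD to NE.

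| | Fallback PD | Fallback NE |
|---|---|---|
| ORR | 77/210 = 36.7% (30.1, 43.6) | the same |
| DCR | 147/210 = 70.0% (63.3, 76.1) | the same |
| BOR of PD | 50/210 = 23.8% | 40/210 = 19.0% |
| BOR of NE | 13/210 = 6.2% | 23/210 = 11.0% |

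**4. When is the PD branch reached?**

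Scans are every 6 weeks ± 7 days from Cycle 1 Day 1. The first falls on days 42 ± 7 = 35 to 49 (15 days) and the second on days 84 ± 7 = 77 to 91. Let m be the minimum SD duration, measured from the start of treatment (assumed, since none is given). A response at the first scan falls short of m on the window days before m.

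| Assumed m (days) | First-scan window days short of m | Second-scan window days short of m |
|---|---|---|
| 28 or 35 | 0 of 15 | 0 |
| 42 | 7 of 15 | 0 |
| 49 | 14 of 15 | 0 |
| 56 | 15 of 15 | 0 |

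The branch also needs no later evaluable scan, because BOR is settled only when all of a subject's data are known.

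**The case against.** The strongest reply is that the NE and PD rules govern single time points, whereas Table 10.5 derives a different quantity. A conservative default for an unconfirmed response breaks no time-point rule. That is fair as far as it goes: the fallback is better described as unsupported by the definitions than as breaching one of them. It still does not fit a BOR defined as the best response recorded.

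A second reply is that the answer may lie elsewhere. Section 10.4 says that it only highlights parts of RECIST v1.1, Table 10.5 cites the published guideline as its source, and Section 9.5 leaves missing-data procedures to a SAP still to be finalised. The guideline is not available here and nothing above relies on it. Deferral to a later document does not correct the two printed rows.

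A third reply is that the harm is limited, and this stands. Section 9.5.1 does not list a BOR frequency table, although such a table usually accompanies ORR. Subjects who stop treatment without BICR progression continue to be scanned, so one missed scan need not settle the BOR.

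A reader might infer more than the documents support:

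- *Every response followed by NE becomes PD.* It does not. SD comes first, and PD applies only below the SD minimum.
- *The primary result is biased.* It is not, by step 3 of the working.
- *Biomarker or exposure-response analyses would label early responders as resistant.* The planned HER3 correlations use ORR, DoR and PFS. The exposure-response modelling is optional and names no BOR category. The exploratory biomarker objective mentions resistance but does not tie it to BOR categories.
- *A sizeable share of subjects is affected.* The documents give no basis for any frequency.

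**Conclusion.** The PD fallback in the CR-then-NE and PR-then-NE rows is wrong as written. Under the appendix's own definitions the result below the SD minimum should be NE.

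The consequence is confined to the BOR distribution, where PD is overstated and NE understated by 0.48 points per affected subject at 210 per arm, and to agreement between BOR and the PFS record. ORR and its test, DCR, PFS and DoR are unaffected.

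The number of subjects is probably small, since the branch needs an early response, no later evaluable scan and a response date before the SD minimum. It cannot be calculated without that minimum. The reach figures assume that the minimum runs from the start of treatment and that scans fall within their windows; an unscheduled scan before day 35 could reach the branch at a shorter minimum. This is a minor but clear correction.

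**What to change.** 1. In Table 10.5, rows CR then NE and PR then NE, keep the SD branch and change the fallback from PD to NE. Leave the other rows as they are.
2. State the minimum SD duration, measured from the start of treatment, in the protocol or SAP. Without it the branch cannot be programmed. The same value decides who counts as SD for DCR, so it should be fixed before the data are examined.
3. Program both the BICR and the Investigator BOR derivations to this rule, with a check that every BOR of PD has a documented progression date.

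The cost is two table cells, one stated value and a small programming change. Section 10.1.1 allows changes to the planned analysis to be documented in an amendment and/or the SAP, and Section 9.5 has the SAP finalised before database lock. The rule can therefore go into the SAP now and the table be corrected at the next amendment, which avoids a separate ethics submission for this alone. Sample size, alpha and power do not change.
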